12.4.1.3 Labelling

The packaging and labelling of bulk drugs will be performed by Investigational Products (IPS), AstraZeneca R&D. Labelling will be in accordance with GMP and local regulatory guidelines. The label will fulfil GMP Annex 13 requirement for labelling.

The investigational product will be supplied as bulk supply to the hospital pharmacy. Each vial containing drug substance will be labelled with a tear-off label. The vials will be packed in boxes.

Individual dosing containers with dispensed solution for nebulisation will be labelled with study specific information. The label will have a tear-off label to be inserted in a separate administration record.

12.4.1.4 Storage

All investigational products must be kept in a secure place under appropriate storage conditions. A description of the appropriate storage and shipment conditions are specified on the investigational product bottle label.

12.4.1.5 Accountability

The medication provided for this study is for use only as directed in the clinical study protocol. At completion of the study unused investigational products will be returned to Investigational Products (IPS), AstraZeneca R&D. The Pharmacy personnel will account for all drugs dispensed and returned. Certificates of delivery, destruction and return must be signed.

12.4.2 Doses and treatment regimens

Single doses of AZD3199 and placebo will be administered as a nebulised solution for inhalation. Planned doses for Part B in this study are placebo and 1 low and 1 high dose of AZD3199 administered to two cohorts of patients with asthma. The starting dose will not exceed half the dose showing systemic pharmacological activity in the healthy subjects. If no systemic pharmacological effects are seen after Dose 5 in Part A, Part B in patients will be initiated with a starting dose of at most half of Dose 5.

12.4.2.1 Adjustment of dose levels

The planned dose levels may be changed or postponed during the course of the study depending on safety, efficacy and pharmacokinetic results obtained. The SRC will make a safety evaluation between each dose level and change the dose escalation if necessary, see Section 15.6. The SRC makes all decisions regarding modification of dose levels.

If no systemic pharmacological effects are seen after Dose 5 in Part A, Part B in patients will be initiated with a starting dose of at most half of Dose 5. Based on preclinical data the therapeutic lung dose of AZD3199 has been estimated to 35 μ g, ie, about the proposed Dose 3 in Part A.

In order to maximise the possibility to assess graded dose - bronchodilatating response, previous experience suggest that the high dose increment should be at least 4 times the low.

After each SRC evaluation personnel dispensing investigational product at the hospital pharmacy and the personnel at IPS, AstraZeneca R&D will be informed about the decision for the next dose escalation and IPS will issue a corresponding dosing schedule.

Approved

Date Printed:

12.4.2.2 Preparation of solution for nebulisation

Dose preparation will take place at the hospital pharmacy according to separate handling instructions and dose confirmation. The powder for solution will be constituted with Sodium chloride for Injection to a stock solution of 3 to 5 mg/mL. For doses requiring a lower concentration the stock solution can be diluted with sodium chloride for injection. The doses, placebo and active drug, respectively, will be dispensed in individual dosing containers. Before drug administration personnel at the clinic will transfer the solution from the individual dosing container to the nebuliser cup.

12.4.2.3 Administration of dose

The subjects will practice inhalation technique on Visit 2 and also on Visit 3 - 5, before the dose will be inhaled.

Administration of dose at the clinic including inhalation procedure will be performed according to detailed separate instructions.

In order to avoid contamination particularly of plasma samples intended for drug analysis the following precautions will be taken: Dosing will take place in a separate inhalation room. Furthermore, subjects and personnel involved in the study drug administration must wear protective gloves and clothing. Personnel involved with drug administration should not be involved with blood sampling.

The study drug will be administered in the morning. The subject will inhale the drug/placebo solution via Spira Electro 2 dosimeter in a sitting upright position. The number of inhalations from the dosimeter required to administer the planned dose will be written on the label of the individual dosing containers. After inhalation the subjects will take off the protective gloves and clothing and wash the outside and around their mouth and their hands before leaving the inhalation room. As soon as possible after this a PK sample will be drawn.

After inhalation, aerosol from the dosimeter may be withdrawn to a collection filter for subsequent analysis and calculation of the actual output from the dosimeter.

12.4.3 Method of assigning patients to treatment groups

Informed consent will be obtained before enrolment and the patients in Part B will be identified with an enrolment number starting with E0002001. Patients fulfilling the eligibility criteria will be assigned patient numbers starting with number 011 for cohort 1, and number 021 for cohort 2 in Part B.

Patients will be assigned patient numbers strictly sequentially as patients are eligible for inclusion in the study. If a patient discontinues from the study the patient number will not be re-used and the patient will not be allowed to re-enter the study.

AN ELECTRONIC DOCUMENT. PLEASE CHECK ITS VALIDITY BEFORE USE

A PRINTED COPY OF

5 H

THIS

12.4.4 Blinding and procedures for unblinding the study

12.4.4.1 Methods for ensuring blinding

The study is single-blind and the patients will not know in which order they receive the placebo dose and the low and high doses of AZD3199.

The active and the placebo doses will be of the same volume, and the same number of inhalations from the solution for nebulisation will be performed to ensure the blinding. Individual dosing containers must be labelled AZD3199/placebo in order to keep the patients blinded.

AstraZeneca personnel and study site personnel will know which dose is administered.

12.4.5 Concomitant medication

The patients must be instructed that no additional medication will be allowed without the prior consent of the investigator.

Any medication, which is considered necessary for the patient's safety and well-being, may be given at the discretion of the investigator(s). The administration of all medication (including investigational products) must be recorded in the appropriate sections of the case report form (CRF).

Medication allowed prior to and during Visits 2-6:

- inhaled corticosteroids $\leq 1000 \ \mu g$ per day, nedocromil and disodium cromoglycate if the dose is kept constant the last 30 days prior to Visit 2 and during the entire study
- immunotherapy treatment if the dose is kept constant ≥90 days prior to Visit 2 and during the entire study
- leukotriene antagonists and 5-lipoxygenase inhibitor if the dose is kept constant

Medication with restricted use prior to and during Visits 2-6:

- inhaled short-acting β_2 -agonists not allowed ≤ 8 hours prior to dose
- inhaled long-acting β_2 -agonists not allowed ≤ 24 hours
- oral β_2 -agonists, short-acting not allowed ≤ 12 hours
- oral β_2 -agonists, short-acting sustained release not allowed ≤ 24 hours

- oral β_2 -agonists, long-acting not allowed ≤ 72 hours
- inhaled anticholinergics not allowed ≤ 12 hours, tiotropium not allowed ≤ 48 hours
- Xanthine containing derivates not allowed \leq 48 hours
- antihistamines not allowed \leq 48 hours

Medication not allowed prior to and during Visits 2-6:

• oral and parenteral steroids are not allowed within 30 days prior to Visit 2

12.4.6 Treatment compliance

Compliance will be assured by supervised administration of the investigational product by the investigator or his delegate. Details of dosing (time, date) will be captured electronically. Tear-off labels will be inserted in separate administration records.

13. PART B - MEASUREMENT OF STUDY VARIABLES

The following study measurements will be obtained. The timing of these measurements is detailed in Table 6 and in Table7. The following 'priority order' will be in effect when more than 1 assessment is required at a particular time point occurs:

- 1. ECG recordings
- 2. Blood pressure, pulse
- 3. Blood sampling
 - Blood sampling for potassium and lactate concentrations
 - Blood sampling for safety laboratory assessments
 - Blood sampling for PK (except blood samples directly after inhalation which may be taken as soon as possible, before any other assessments)
- 4. Assessment of palpitations and tremor
- 5. Spirometry

74(95)

13.1 Medical examination and demographic measurements

13.1.1 Enrolment medical examination and demographic measurements

Each patient will undergo an enrolment medical examination at Visit 1 and 2 within 30 days prior to the treatment visit. This will consist of:

- Recording of demographic data date of birth, sex, height, weight, race
- A standard medical/surgical history and a physical examination including the cardiovascular and respiratory systems
- A resting 12-lead ECG
- A resting blood pressure and pulse
- Laboratory assessments (clinical chemistry, haematology and urinalysis)
- A blood sample for HIV, Hepatitis B and C test
- Drugs of abuse screen and alcohol breath test
- Review of inclusion and exclusion criteria
 - Spirometry
- Stepwise reversibility test

13.1.2 Post-study medical examination

A follow-up medical examination will be performed at Visit 6 within 10 ± 3 days after the last administration of study drug. This will consist of:

- A physical examination
- A resting 12-lead ECG
- A resting blood pressure and pulse
- Laboratory assessments (clinical chemistry, haematology and urinalysis)
- Spirometry
- Reversibility test with formoterol
 - Collection of adverse events

AN

ЪО

PRINTED COPY

TS A

THIS

ELECTRONIC DOCUMENT. PLEASE CHECK ITS VALIDITY BEFORE USE

Approved

Date Printed:

13.2 Pharmacokinetic measurements

13.2.1 Determination of drug concentration in biological samples

Samples for measurement of drug concentration will be analysed by a method using HPLC/MS/MS. Details of the methods used will be referred to in the clinical study report.

13.2.2 Collection of biological samples

13.2.2.1 Blood sampling for AZD3199 plasma concentration

Blood samples (3 mL) for determination of AZD3199 in plasma will be taken at the times presented in Table 7. PK analysis during the study may indicate that the sampling schedule is sub-optimal and therefore additional samples may be taken, samples may be omitted, and/or the times of sampling may be adjusted. Blood samples will be collected, labelled and shipped according to separate instructions from the laboratory. The date and time of collection will be recorded in the CRF.

Samples should be stored at -20°C or below and analysed within the time frame after collection for which the stability in the samples has been validated and found acceptable. Results from analyses stored longer than the period stated will not be reported.

The disposal of samples will be decided within 1 month after the clinical study report has been finalised.

13.3 Pharmacodynamic measurements

13.3.1 Spirometry

13.3.1.1 Assessment of FEV₁

Spirometry for determination of FEV_1 and FVC will be performed at enrolment and follow-up. During treatment visits, Visits 3-5, only FEV_1 will be measured (see Table 6 and Table 7).

Lung function testing will be performed according to ERS recommendations (Quanjer et al 1993). The spirometer should be calibrated according to instructions. The highest FEV_1 and FVC out of 3 measurements will be recorded. The highest and the second highest FEV_1 values must not differ by more than 5%. If the difference is larger than 5% the patient may perform up to 8 measurements. If the variation is still above these limits, the largest value will be recorded with a comment.

13.3.1.2 Reversibility tests

Stepwise reversibility test

A stepwise reversibility in FEV₁ will be assessed at Visit 2. After baseline FEV₁ is recorded, the patient will inhale 100 μ g salbutamol via *pMDI* and FEV₁ will be recorded 15 - 30 minutes later. The subject will then inhale 900 μ g salbutamol and FEV₁ will be recorded 15 - 30 minutes later. An minimum of 5% additional increase from the first dose and a total of at least 15% increase in FEV₁ relative to baseline are required.

Reversibility test with formoterol

Reversibility in FEV₁ after formoterol will be assessed at Visit 6. After baseline FEV₁ is recorded the patient will inhale 2 x 4.5 μ g formoterol via Turbuhaler and FEV₁ will be recorded 15 - 30 minutes later.

13.3.2 Assessment of tremor and palpitations

Tremor and palpitations will be assessed by a scoring question. The patient will be asked to estimate the tremor and palpitations by using a 4-grade scale; no, mild, moderate or severe. For timepoints of assessments see Table 7.

13.3.3 Potassium concentrations

Blood will be drawn in order to determine potassium concentrations and sent to the local laboratory at the hospital for analysis. Blood must be sampled without stasis and handled gently according to separate instructions in order to avoid haemolysis. Samples will be collected at the times given in Table 7.

13.3.4 Lactate concentrations

Blood will be drawn in order to determine lactate concentrations and will be sent to the local laboratory at the hospital for analysis. Blood must be sampled without stasis and handled gently according to separate instructions in order to avoid haemolysis. Samples should be put on ice prior to being processed. Samples will be collected at the times given in Table 7.

13.3.5 QTc and Heart rate

QT and heart rate will be extracted from the 12-lead ECG measurements. For timepoints of assessments see Table 7.

13.3.6 Blood pressure

Supine blood pressure (BP) will be measured using an semi automatic blood pressure recording device with an appropriate cuff size. The equipment and method of obtaining BP and pulse shall be consistent for all patients in the study. BP will be measured after the patient has rested in bed for at least 10 minutes, at the times given in Table 7.

77(95)

13.4 Safety measurements

13.4.1 Laboratory safety measurements

Blood and urine samples for determination of clinical chemistry, haematology and urinalysis parameters will be taken at the times given in Table 6 and Table 7. The date and time of collection will be recorded on the appropriate CRF (at Visit 1, 2 and 6 only date).

Patients should rest at least 3 minutes in the supine position before blood sampling. Samples will be collected in tubes according to standard routines. See Section 13.5 for information on the volumes of blood to be taken.

The following laboratory variables will be measured:

Clinical chemistry (serum or plasma)	Haematology (whole blood)
S/P-Creatinine	B-Haemoglobin (Hb)
S/P-Bilirubin (total) (Bil, tot)	B-Platelet count
S/P-Alkaline phosphatase (ALP)	B-Leucocyte count (LPC)
S/P-Aspartate aminotransferase (AST)	B-Leucocyte differential count
S/P-Alanine aminotransferase (ALT)	
S/P-Albumin	
S/P-Potassium (K)	Urinalysis
S/P-Calcium (total) (Ca)	U-Protein/Albumin
S/P-Sodium (NA)	U-Hb/Erythrocytes/Blood
S/P-Glucose	U-Glucose
S/P Thyroxine free (T4)	
S/P Thyroid-stimulating hormone (TSH)	
S/P-C-Reactive Protein (CRP)	

All samples will be handled and analysed by a local hospital laboratory, except for the urinalysis (dipstick) that will be analysed at the study site according to local procedures.

13.4.1.1 HIV, Hepatitis B and C test

For safety of the study site staff, all patients will be tested for antibodies to HIV, hepatitis B surface antigen and for antibodies to hepatitis C virus at Visit 1. If a patient is found positive to any of these tests, he will be referred for further examination and treatment and will not be included in the study. The samples will be handled and analysed at a local hospital laboratory.

Results will not be recorded in the CRF.

13.4.1.2 Drugs of abuse and alcohol testing

A drug screen (cannabis, methamphetamines, opiates, cocaine, methadone, benzodiazepines, barbiturates, tricyclic anti depressants, phencyclidine (PCP), and amphetamines) in the urine will be done at Visit 1 and once randomly at any of Visits 3-5 in order to exclude or withdraw patients with drug abuse. The samples will be analysed according to local routines.

A breath alcohol test will be performed at Visit 2 and randomly at Visits 3-5.

If a patient tests positive in the drugs of abuse test, a confirming test will be sent to a local hospital laboratory. If the drug is illegal, counselling and advice will be offered.

Results will not be recorded in the CRF.

13.4.2 Electrocardiographic measurements

13.4.2.1 Resting 12-lead ECG

PLEASE CHECK ITS VALIDITY BEFORE USE

ELECTRONIC DOCUMENT.

AN

ЪО

PRINTED COPY

IS A

THIS

12-lead ECG recordings will be obtained after 10 minutes rest in the supine position, at the time points indicated in the time plans (see Table 6 and Table 7). The patient must have the same position (max 30 degrees) during all ECG registrations. A print out at paper speed 50 mm/sec will be used. Heart rate, QT and an overall evaluation, normal / abnormal (specified) will be recorded in the CRF for ECGs collected predose, and 30 minutes to 12 h post dosing. For ECGs collected at Visits 2 and 6 and the 48 h post dose ECGs at Visits 3-5 only an overall evaluation, normal/abnormal (specified) will be recorded.

13.4.2.2 Real-time display (telemetry)

A real-time ECG will be displayed for at least 48 hours at Visits 3 - 5 starting within 1 hour before the intake of investigational product, according to local routines at the clinic, and will be monitored by the investigator or his/her delegate. The time might be adjusted once more information about the compound characteristics are available.

Date and time for start and end of measurement will be collected in the CRF. Clinically relevant findings should be documented as AEs in the CRF, at the discretion of the investigator or his/her delegate.

Short time periods off telemetry are permitted at the discretion of the investigator.

13.4.3 Vital signs

13.4.3.1 Blood pressure and pulse

For timing of individual measurements refer to Table 6 and Table 7.

Approved

Date Printed:

Supine blood pressure and pulse will be measured after the patient has rested in bed for at least 10 minutes. Blood pressure and heart rate (HR) will be measured using a semi-automatic blood pressure recording device with an appropriate cuff size. The equipment and method of obtaining blood pressure and pulse shall be consistent for all patients in the study. At Visits 3-5, all data will be captured electronically.

13.4.4 Other safety measurements

13.4.4.1 Lung function tests - Spirometry

Spirometry for determination of FEV_1 and FVC will be performed at enrolment and follow-up. During treatment visits, Visits 3-5, only FEV_1 will be measured. Spirometry measurements are described in Section 13.3.1.

13.4.4.2 Physical examination

The physical examination will include: general appearance, skin, mouth, teeth and throat, lymph nodes, thyroid, musculoskeletal/extremities, cardiovascular, lungs, abdomen and neurological. The examination will be carried out at enrollment and follow-up visit (see Table 6) according to the normal routines at the study site.

13.5 Volume of blood sampling

The total volume of blood that will be drawn from each patient in this study is as follows:

Assessment		Sample volume (mL)	n of samples	Total volume (mL)
Safety	clinical chemistry	3	14	41
	Glucose	2	14	28
	haematology	2	14	28
Pharmacokinetics (AZD3199) ^a		3	28	84
Pharmacodynamics	Potassium	3	39	117
	Lactate	2	15	30
Pharmacogenetics ^b		10	1	10
HIV/Hepatitis B and C		7	1	7
Total				345

Table 10	Part B - Volume of blood to be drawn from each patient
----------	--

a The number of samples may be modified during the course of the study, see Section 13.2.2.1, but the total blood volume taken in the study will not exceed 450 mL.

b The pharmacogenetics part is described in detail in Appendix D

Approved

Date Printed:

13.6 Adverse Events

The methods for collecting adverse events are described below.

13.6.1 Adverse Events

13.6.1.1 Definitions

The definitions of AEs, serious adverse events (SAEs) and other significant adverse events (OAEs) are given below. It is of the utmost importance that all staff involved in the study are familiar with the content of this section. The principal investigator is responsible for ensuring this.

Adverse event

AN ELECTRONIC DOCUMENT. PLEASE CHECK ITS VALIDITY BEFORE USE

PRINTED COPY OF

R

ы И

THIS

An adverse event is the development of an undesirable medical condition or the deterioration of a pre-existing medical condition following or during exposure to a pharmaceutical product, whether or not considered causally related to the product. An undesirable medical condition can be symptoms (eg, nausea, chest pain), signs (eg, tachycardia, enlarged liver) or the abnormal results of an investigation (eg, laboratory findings, electrocardiogram). In clinical studies, an AE can include an undesirable medical condition occurring at any time, including run-in or washout periods, even if no study treatment has been administered.

Serious adverse event

A serious adverse event is an AE occurring during any study phase (ie, run-in, treatment, washout, follow-up), and at any dose of the investigational product, comparator or placebo, that fulfils 1 or more of the following criteria:

- Results in death
- Is immediately life-threatening
- Requires in-patient hospitalisation or prolongation of existing hospitalisation
- Results in persistent or significant disability or incapacity
- Is a congenital abnormality or birth defect
- Is an important medical event that may jeopardise the patient or may require medical intervention to prevent 1 of the outcomes listed above.

The causality of SAEs (ie, their relationship to study treatment) will be assessed by the investigator(s), who in completing the relevant case report form must answer "yes" or "no" to the question "Do you consider that there is a reasonable possibility that the event may have been caused by any of the following - study medication - other medication?" For further

81(95)

guidance on the definition of an SAE and a guide to the interpretation of the causality question, see Appendix B to the Clinical Pharmacology Study Protocol.

Note that SAEs that could be associated with any study procedure should also be reported. For such events the causal relationship is implied as "yes".

Other Significant Adverse Events (OAE)

OAEs will be identified by the Study Delivery Team Physician in consultation with the appropriate Global Drug Safety Physician during the evaluation of safety data for the Clinical Study Report. Significant adverse events of particular clinical importance, other than SAEs and those AEs leading to discontinuation of the patient from study treatment, will be classified as OAEs. Examples of these are marked haematological and other laboratory abnormalities, and certain events that lead to intervention (other than those already classified as serious), dose reduction or significant additional treatment. For each OAE, a narrative may be written and included in the Clinical Study Report.

13.6.1.2 Recording of adverse events

AEs including SAEs will be collected from time of signed informed consent until the end of study. However, the first AE questioning will be done at Visit 3.

Symptoms

AEs will be collected by means of 3 standard questions. The questions will be put to each patient in Swedish. The question "Have you had any health problems since the first visit?" will be put to each patient when they arrive at the clinic at Visit 3. The question "Have you had any health problems since you were last asked?" will be put to each patient at set times after study drug administration at Visits 3-5 (see Table 7). Furthermore, the question "Have you had any health problems since the previous visit?" will be put to each patient upon arrival to the clinic at Visits 4-6. The timing of these questions may be changed during the study, to reflect the safety and pharmacokinetic data produced during the study. The patient's response to these questions and spontaneously reported and/or observed AEs will be recorded on the AE form with information about seriousness, causality, action taken, date (and time, if starting during a clinic visit) of onset, date (and time, if ends at a visit) of recovery (or marked as ongoing), intensity and outcome.

Causality

The causality of all AEs (ie, the relationship to study treatment) will be assessed by the investigator(s), who in completing the relevant case report form must answer "yes" or "no" to the question "Do you consider that there is a reasonable possibility that the event may have been caused by the investigational product?" A guide to the interpretation of the causality question is found in Appendix B.

82(95)

Intensity

The patients will be asked to assess the intensity of the reported AEs according to the following scale:

- mild (awareness of sign or symptom, but easily tolerated)
- moderate (discomfort sufficient to cause interference with normal activities)
- severe (incapacitating, with inability to perform normal activities)

It is important to distinguish between serious and severe AEs. Severity is a measure of intensity whereas seriousness is defined by the criteria in Section 13.6.1.1. An AE of severe intensity need not necessarily be considered serious. For example, nausea that persists for several hours may be considered severe nausea, but not an SAE. On the other hand, a stroke that results in only a limited degree of disability may be considered a mild stroke but would be an SAE.

Assessment of tremor and palpitations

In order to evaluate the expected tremor and palpitations after inhalation of β_2 -agonists, questions will be put to the patients at specified timepoints (see Table 7). The presence and, if applicable intensity, of the symptom will be recorded according to the following scale: No, Mild, Moderate or Severe.

Symptoms emerging from the above specified active questioning are not to be recorded as AEs on the AE form unless:

• the symptom is serious according to definitions, see Section 13.6.1.1

or

the subject discontinues the study due to the symptom

Symptoms of the disease under study - Asthma

Asthma symptoms or signs, such as chest tightness, cough, dyspnoea, sputum increased and wheeze, will be recorded as AEs when:

the sign or symptom is serious according to definitions, see Section 13.6.1.1

or

•

the subject discontinues the study due to the sign or symptom

Approved

Date Printed:

and/or

the sign or symptom is new to the subject or not consistent with the subject's pre-existing asthma history (defined as within 1 year of Visit 1) as judged by the investigator

Abnormal findings

During the study, abnormal laboratory results, pulse, blood pressure, FEV_1 and FVC, and ECG are not to be recorded as AEs in the CRF unless they result in discontinuation or represent SAEs, or the investigator judges them to be of such clinical importance as to merit recording as AEs.

The investigator will review results from physical examination. All new and/or aggravated findings (at follow-up) as compared with baseline measurement (at screening visit) must be identified and recorded on the AE form. These will be considered AEs.

Concomitant medication

All changes in the patient's medication, eg, dose change or addition of new medication, must be reported in the medication log. Reasons for changes in medication, which reflect an AE, must be recorded on the AE form.

Unresolved AEs

If an AE is unresolved when the study is terminated, its subsequent course must be followed until the AE subsides or until the investigator decides that no further follow-up is necessary. However, more information about such AEs may be requested.

Overdose

Should an overdose (accidental or deliberate) occur, it must be reported in accordance with the procedures described in Section 17.3, Procedures in case of overdose, regardless of whether the overdose was associated with any symptom or not. All symptoms associated with the overdose should be reported as AEs.

Coding of AEs

AstraZeneca will code AEs by using the Medical Dictionary for Regulatory Activities (MedDRA).

MedDRA includes 5 levels: lowest level terms, preferred terms, high level terms, high level group terms, and system organ class terms. Lowest level terms are used on the input side (data entry) to reflect as closely as possible the term used by the investigator or patient to describe the event. Preferred terms are mainly used on the output side (data presentation) to

group terms that are synonymous or closely related. High level terms and high level group terms are also used on the output side. System organ class terms group AEs pertaining to the same body system.

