12.2.2 Risk/benefit and ethical assessment

The patients will have no individual benefits. Before inhaled doses of AZD3199 are administered to patients with asthma, the same or higher doses have been evaluated in healthy volunteers.

There are several inhaled LABAs in clinical used and under development for the treatment of asthma and COPD. The most cited adverse effects are palpitation, headache and tremor. At higher doses tachycardia, hyperglycemia, hypokalemia and an increased QTc interval may be seen.

The most important adverse effects observed in the non-clinical studies with AZD3199 with potential relevance for humans are: signs of irritation in the nose and larynx in the rat and heart rate increase, QTc prolongation and decrease in plasma potassium in the dog. These effects can easily be monitored in the clinical study and are not considered to pose any safety concerns.

For an overall risk benefit assessment see the Investigator's Brochure.

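### Part B's asthma-symptom rule can keep non-serious cough, wheeze or chest tightness that starts or worsens after inhalation off the adverse-event form, on an unblinded judgement of consistency with asthma history

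*Protocol*

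**What the plan says.** Section 12.2.2 of the protocol, the Part B risk/benefit assessment, includes "signs of irritation in the nose and larynx in the rat" among the most important non-clinical effects of possible human relevance. Of the listed effects together it says: "These effects can easily be monitored in the clinical study and are not considered to pose any safety concerns".

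Section 13.6.1.2 (Part B), under symptoms of the disease under study, states: "Asthma symptoms or signs, such as chest tightness, cough, dyspnoea, sputum increased and wheeze, will be recorded as AEs when" at least one of three conditions holds:

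- "the sign or symptom is serious according to definitions, see Section 13.6.1.1"
- "the subject discontinues the study due to the sign or symptom"
- "the sign or symptom is new to the subject or not consistent with the subject's pre-existing asthma history", where history means within one year of Visit 1 and the investigator judges.

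Section 13.6.1.1 defines an adverse event more widely. It includes the worsening of a condition the patient already had, during or after exposure, whatever the cause.

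On blinding, section 12.4.4.1 says: "AstraZeneca personnel and study site personnel will know which dose is administered". Section 11.2 makes the incidence and nature of AEs part of Part B's first secondary objective. Sections 12.1.1 and 15.6 put AEs among the data the Safety Review Committee (SRC) uses before each escalation.

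**The concern.** Every Part B patient has asthma, and the drug is a nebulised solution. Cough, chest tightness, dyspnoea, increased sputum and wheeze are among the symptoms that airway irritation by the inhaled dose could produce. They are also the symptoms the rule filters. None of the three conditions refers to onset after inhalation, to worsening, or to suspected relation to the drug. A patient who usually coughs, and who coughs more after the high dose without it being serious or making him stop, need not appear on the AE form.

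Two things are at stake. The AE table is where local tolerability in patients with asthma will be read, and the SRC sees AEs when it decides on the next dose. The judgement of consistency is also made by someone who knows whether placebo, low dose or high dose was given. The same symptom could be classified differently at Visits 3, 4 and 5, which would distort the comparison within patients. An analysis plan cannot repair this later, because the event would never have been collected.

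**Working it through.** The protocol gives no figure to reproduce, so the check is a comparison of sections.

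**1. Rule against definition.** Under 13.6.1.1, asthma cough that worsens after dosing is an AE. Under 13.6.1.2 it is an AE only if serious, if it causes discontinuation, or if the investigator finds it new or inconsistent with history. The two agree only if the investigator treats post-dose worsening as inconsistent. The text permits that reading but does not require it.

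**2. Rule against the monitoring statement.** Section 12.2.2 relies on "These effects can easily be monitored in the clinical study". The possible routes at Visits 3-5 are:

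- Standard AE questions and spontaneous reports (13.6.1.2): open for nasal irritation, hoarseness and sore throat; filtered for the listed asthma symptoms.
- Symptom scoring after dosing (13.3.2, Table 7): covers tremor and palpitations only. Those symptoms are also kept off the AE form by default, but their four-grade score replaces the missing record. The airway symptoms have no such replacement.
- Throat examination (13.4.4.2): at enrolment and follow-up, not on dosing days.
- FEV1 (Table 7): read at 10, 30 and 60 min and later. By 13.6.1.2 an abnormal value is not an AE unless it leads to discontinuation, is an SAE, or is judged clinically important.

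**3. What FEV1 can show.** Section 15.1.2 derives the maximum, the average and the 22-26 h effect. A maximum does not show a brief early fall, and an average dilutes it. Values at each time are also analysed, with the stated purpose of following duration of effect, so an early fall would be visible there. Section 12.2.1 says this drug class relaxes the airways whatever caused the constriction, so the drug's own action could offset irritant narrowing. Cough without a fall in FEV1 would not show at all.

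**4. Illustration only.** The protocol gives no rates. Assume the high dose causes one of the listed symptoms, non-serious and without discontinuation, in 30% of the 8 patients in a cohort. Assume also that a fraction f of cases is judged consistent with history and so not recorded.

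P(at least one recorded) = 1 − (1 − 0.30 × (1 − f))^8; expected recorded cases = 8 × 0.30 × (1 − f).

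| f | P(at least one recorded) | Expected recorded cases |
|---|---|---|
| 0 | 1 − 0.70^8 = 0.942 | 2.4 |
| 0.5 | 1 − 0.85^8 = 0.728 | 1.2 |
| 0.75 | 1 − 0.925^8 = 0.464 | 0.6 |
| 0.9 | 1 − 0.97^8 = 0.216 | 0.24 |

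Both inputs are assumptions. Having had a symptom in the past year does not exclude it automatically, because the test is consistency with the patient's pattern. So f cannot be read off a prevalence of past symptoms.

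**The case against.** The strongest case against runs as follows. The rat finding concerns the nose and larynx, and nothing in the protocol says it would appear in patients mainly as chest tightness or wheeze; typical nose and throat complaints lie outside the rule. The wording on inconsistency lets an investigator record cough that follows inhalation or is worse than usual. Serious symptoms and those causing discontinuation are always recorded. FEV1 is analysed by time, and the SRC reviews lung function up to 26 h (15.6). Part A is double-blind, has no asthma filter (4.6.1.2), includes spirometry at 10 min, 1 h and 6 h (Table 2), and covers each Part B dose at an equal or higher level (12.2.1). Keeping symptoms of the studied disease out of the AE table is a deliberate choice, and bronchodilators are withheld before sessions (12.4.5), so recording every symptom adds background events.

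Most of this stands, and it narrows the point. It does not close it. Permission to call a post-dose symptom inconsistent is not an instruction to do so, and the person deciding is unblinded. Part A studies healthy men, so it cannot show how asthmatic airways react.

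A reader might infer that the Part B AE table will miss drug-induced irritation altogether, or that the rule flatly contradicts the AE definition. The documents support neither. Several routes to recording stay open, and the conflict arises only when worsening is judged consistent with history.

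**Conclusion.** The point holds as a limited gap in AE capture. It concerns non-serious cough, chest tightness, dyspnoea, increased sputum or wheeze that starts or worsens after inhalation, in patients who continue, when an unblinded investigator judges it consistent with the past year's asthma history. For these events 13.6.1.2 does not secure what 13.6.1.1 defines as an AE, and no symptom score or throat examination on dosing days stands in for the record. The gap bears on Part B's first secondary objective and on AE data used for escalation.

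Its size is unknown. The range of 22% to 94% above shows only how strongly the chance of seeing a signal in 8 patients depends on the filter, under an assumed 30% incidence. It does not estimate what this study will miss. Nor does the protocol say that irritation will be missed; it says the effects can be monitored, and in part they can.

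**What to change.** Reconcile 12.2.2, 13.6.1.1 and 13.6.1.2. In 13.6.1.2, state that at Visits 3-5 any listed symptom that starts or worsens after inhalation of study drug, up to the end of the 48 h stay, is recorded with its onset time whatever the asthma history. The existing exemption can remain for the time outside treatment sessions.

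Tabulate these events by treatment (placebo, low, high). Note with the table that placebo is always given at Visit 3 and that staff are unblinded. The placebo session gives context for background asthma, but the comparison is confounded with period and open to reporting bias.

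Add to 15.2.1 a summary of the lowest FEV1 in the first hour relative to the same visit's pre-dose value, from the 10, 30 and 60 min readings already scheduled.

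The cost is a wording change, two extra summaries and more AE rows that reflect ordinary asthma. No visit or procedure is added, and no dose, treatment or stopping rule changes.
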